10.3. Adverse Event Management – Study Medication

Definition of adverse event (AE): Any untoward medical occurrence in a participant or clinical investigation subject administered/using a product and which does not necessarily have to have a causal relationship with this treatment. An adverse event can therefore be any unfavourable and unintended sign (including an abnormal laboratory finding), symptom, or disease temporally associated with the use of a product, whether or not considered related to the product. Hyperglycaemia and hypoglycaemia handled by the safety procedures are not considered as AE.

Definition of serious adverse event (SAE): An adverse event that results in death, is life threatening (note: the term life-threatening refers to an event in which the participant was at risk of death at the

time of the event; it does not refer to an event which hypothetically might have caused death if it was more severe), requires inpatient hospitalization or results in prolongation of existing hospitalization, results in persistent or significant disability/incapacity or is a congenital anomaly/birth defect.

Definition of serious adverse reaction (SAR): A SAE for which a causal relationship to the study medication is at least possible i.e. a causal relationship is conceivable and cannot be dismissed.

Definition of suspected unexpected serious adverse reaction (SUSAR): A SAE which is unexpected and regarded as possibly or probably related to the trial/study product by the Investigator. To evaluate whether the adverse reaction is to be expected Investigator refer to sections 4.8 of the medication summaries for GlucaGen® and FiAsp (attached).

Classification of an AE: Related or not related.

Final outcome classification of an AE: Recovered or not recovered.

Investigations and potential treatment of an AE: Dependent on the investigator's evaluation. Participants experiencing AEs will be monitored until satisfactory stabilization and/or full recovery.

Reporting of AE, SAE, SAR and SUSAR: All events meeting the definition of an AE will be collected and reported. This includes events occurring during the clinical studies i.e. two times 26 hours, and in the 50 minutes following each study (corresponding to five half-times for glucagon). SAEs, SARs, SUSARs will initially be reported to the sponsor within 24 hours after the investigator has become aware. All follow-up data will be described in detail in a SAE-formula and hereafter the formula will be given to the sponsor within 24 hours of obtaining the new knowledge. Previous non-serious AEs, which becomes SAEs follows the reporting of SAEs.

Sponsor will ensure that all information on SUSARs that are fatal or life-threatening is recorded and reported to the Danish Health and Medicines Authority (web-based form) as soon as possible and no later than seven days after the sponsor becomes aware of such possible side effects. Within eight days after reporting, sponsor will provide the Danish Health and Medicines Authority with all relevant information about the sponsor's and investigator's response to the alert and consequences for the further course of the study conduct.

All other SUSARs will be reported to the Danish Health and Medicines Authority within 15 calendar days after sponsor becomes aware of them.

Reporting at the end of the study: All AEs and SAEs will be included and uploaded in the results section of the study EudraCT (<https://eudract.ema.europa.eu/>). The link to this report will be sent to the Danish Health and Medicines Authority and the Regional Scientific Ethics Committee within 12 months after the last participant has completed the project. SARs are reported to the Danish Health and Medicines Authority and the Regional Ethics Committee annually.

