8.2.1.4. Adverse events

- Number of adverse events (event if visual analog scale (0-100) increase >10 from baseline) for
 - Nausea
 - Headache
 - Palpitation
- Number of vomits

8.2.1.5. Other:

- Difference between actual and participant-estimated CHO content in meals
- Mean Borg scale level during exercise

- Physical activity intensity measured by ActiGraph GT9X Link
- Sleep efficiency measured by ActiGraph GT9X Link

Means, medians, percentages, standard deviations, ranges, interquartile ranges and 95% confidence intervals will be calculated for descriptive analyses. All inferential outcome analyses compare single-hormone with dual-hormone closed-loop glucose control using paired t-test for normally distributed data and Wilcoxon signed-rank test when data cannot be assumed to be normally distributed.

* An asterisk indicates that the outcome will be calculated for the whole study period as well as for the following intervals: dinner (19:00-23:00), night (23:00-08:00), breakfast (08:00-12:00), lunch + snack (12-16:30), and exercise session (16:30-19:00).

9. Statistical considerations and power calculation

9.1. Phase 1

Phase 1 is a feasibility study in which we explore operability of our system with special emphasis on safety issues. Reaching statistical significance is not a goal. We choose to include a maximum of four participants with T1D in this phase.

9.2. Phase 2

To be able to detect a difference in percentage of time with glucose values < 3.9 mmol/l (primary outcome) of 2.3 %-points (approximately 30 minutes) with 90% power, a 5%-significance level, and a presumed 3.0 %-points standard deviation, 20 participants should be included in the study (2-sided test). The sample size calculation is partly based on data obtained from our adult study; however, we expect higher variation due to pubertal status.

Participants who drop out of the study will be replaced such that the total number of participants who have completed a single- and a dual-hormone closed-loop study is 20. Only data from participants who have completed a full single- and a full dual-hormone study session will be included in the analysis comparing the two control types. More than 80% of possible sensor values from each study session are required to be included in the analysis. Furthermore, data from completers and non-completers will be stated in the final report.

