For every carbohydrate rescue during the study, 30 minutes of the time in range is allocated to time in hypoglycemia and will be accounted for in the primary analysis. A paired student's t-test will be used to compare the outcomes if data are normally distributed. Otherwise, a Wilcoxon Signed Rank test is be used. In order to account for missing values and adjusting for different factors, a repeated measurement ANOVA will be used with the outcome and adjusting factors as fixed effects and the intercept as a random effect. Bonferroni adjustments will be applied for non-specified outcomes.

Based on previous experience from this type of study we expect a very low drop-out rate, $< 10\%$.

Therefore, a maximum of 24 participants are needed for this project that includes phase 1 (N=4) and phase 2 (N=20).

If it turns out that deviations from the statistical plan described above are necessary, the Danish Health and Medicines Authority, the Regional Scientific Ethics Committee and the GCP-unit will be informed. The original statistical plan as well as the new strategy will be reported in the publication of study results.

10. Safety

For safety reasons, at least one study personnel will always be present during the clinical study.

10.1 Hypoglycemia management:

Hypoglycemia will be managed according to the standard operating procedures (SOP_Dysglycemia). A hypoglycemia episode is defined as one plasma glucose value < 3.0 mmol/l. In the event of a hypoglycemic episode, the attending physician will take immediate action to raise the blood glucose by providing the participant with oral carbohydrate. The treatment will be repeated if the hypoglycemia has not resolved within 15 minutes. Repeated YSI measurement will be performed every 5 minutes until BG is > 3.9 mg/dl (SOP_Dysglycemia).

If at any point during the study the participant experiences symptoms of hypoglycemia and requests oral carbohydrate, a blood sample for plasma glucose determination will be drawn. Irrespective of the plasma glucose value the participant will be treated with oral carbohydrate. However, repeated YSI measurements will only be measured if < 3.9 mmol/l.

If at any point during the study the participant experiences a severe hypoglycemic event, i.e. the participant is unable to take oral CHO, intravenous glucose will be administered via the sampling cannula and the study will be terminated.

10.2. Hyperglycemia management:

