10.4. Adverse Event Management – Medical Devices

The definition of a serious adverse event is given above ('adverse event management – study medication' section). With regard to medical devices, serious adverse events also include situations that could potentially have led to serious adverse events if circumstances had been different or if there

had been no interference, so called near serious adverse events (NSAEs). However, hypoglycaemia and hyperglycaemia events handled according to our safety procedures are not regarded as NSAEs.

Reporting of SAE and NSAE: All events meeting the definition of a SAE or a NSAE will be collected and reported. This includes events occurring during the clinical studies i.e. two times 26 hours. In case of SAE or a NSAE, the primary investigator should be informed within 24 hours (contact information on page 2). All follow-up data will be described in detail in a SAE/NSAE-formula. The primary investigator will ensure that all information on adverse events that are/could have been fatal or life-threatening is recorded and reported to the Danish Health and Medicines Authority (web-based form) as soon as possible and no later than seven days after the event. Within eight days after reporting, sponsor will provide the Danish Health and Medicines Authority with all relevant information about the primary investigator's response to the alert and consequences for the further course of the study conduct.

When reporting SAEs and NSAEs to the authorities the following parameters are included: Study name, participant identification (subject number, initials, sex, age), event (preferably a diagnosis), study medication, reporter identification (name or initials), causality and outcome.

Reporting at the end of the study: All SAEs and NSAEs will be included and be uploaded in the EudraCT. The link will be sent to the Danish Health and Medicines Authority and the Regional Scientific Ethics Committee within 12 months after the last participant has completed the project.

11. Source data

A separate electronic case report form (eCRF, RedCap) will be prepared for each study participant.

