No biobank will be established. All blood samples will be analyzed immediately after they have been drawn and discarded after analyses.

12. Study rescheduling and termination

A study might be discontinued due to technical challenges, adverse events, an episode of severe hypoglycemia or participant request. Rescheduling is possible if the cause of discontinuation is modifiable according to the investigator's assessment.

The study as a whole may be terminated in the event of unresolvable technical issues such as algorithm underperformance or other unforeseen events that by the investigator's evaluation makes study continuation unjustifiable.

If the technical issues require to change the medical devices, the sponsor will send an amendment to the Danish Medical Agency for a renewed approval before study continuation.

14. Time schedule

First participant first visit is expected in April 2021. Last participant last visit is expected in June 2021. Analysis of blood samples and data will be completed before April 2023.

15. Project economy

The project is investigator initiated. Investigator salaries, equipment, medications and consumables are covered by the research unit at Steno Diabetes Center Copenhagen and Technical University of Denmark. None of the investigators have personal financial interest in the conduct or the outcome of the project.

The primary investigator, [name], is employed in a 2-year PostDoc position at Steno Diabetes Center Copenhagen and funded by the Danish Diabetes Academy Grant ID PD002-19. The study has further received a research grant from the Danish Diabetes Association (225,000 DKK).

Further funding will be applied for. If further funding is obtained, the Regional Ethics Committee will be informed, and the participant information will be updated accordingly.

16. Remuneration

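### Sections 10.3 and 10.4 exclude hypoglycaemia from AE and NSAE status without a severity limit, so severe hypoglycaemia treated under section 10.1 is, read literally, not classified as a safety event

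*Combined protocol and SAP*

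**What the plan says.** Section 10.1 (hypoglycaemia management, under section 10, Safety) covers both ordinary and severe episodes. A severe event is described thus: "i.e. the participant is unable to take oral CHO, intravenous glucose will be administered via the sampling cannula and the study will be terminated".

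Section 10.3 (study medication) first defines an AE broadly and then adds: "Hyperglycaemia and hypoglycaemia handled by the safety procedures are not considered as AE". The next definition begins "Definition of serious adverse event (SAE): An adverse event that results in death, is life threatening". SAR and SUSAR are in turn defined as kinds of SAE.

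Section 10.4 (medical devices) takes over the same definition: "The definition of a serious adverse event is given above". It adds the NSAE class, for situations that could have turned out serious in other circumstances or without intervention. It then provides that "hypoglycaemia and hyperglycaemia events handled according to our safety procedures are not regarded as NSAEs".

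Section 9.2 limits the comparison of treatments: "Only data from participants who have completed a full single- and a full dual-hormone study session will be included in the analysis". Drop-outs are replaced until 20 participants have completed both sessions. Section 12 says: "A study might be discontinued due to technical challenges, adverse events, an episode of severe hypoglycemia or participant request". It allows rescheduling if the cause can be modified.

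**The concern.** It is reasonable to keep ordinary, orally treated hypoglycaemia out of the AE count in a trial whose primary outcome is time below 3.9 mmol/l. The two exclusions do not stop there. As worded, they also cover the episode in which a participant aged 13 to 17 cannot take carbohydrate by mouth and needs intravenous glucose.

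Insulin is dosed by an algorithm that section 7.1.4 says is not CE-marked. Section 17 opens its risk assessment with hypoglycaemia caused by an insulin dose based on an inaccurate sensor, and section 1 says untreated hypoglycaemia can lead to seizures, unconsciousness or death. The hypothesis in section 2 is that the system is safe as well as effective. An AE/SAE/NSAE listing that excludes severe hypoglycaemia by rule gives weak support to a statement about safety, and the reader of the results could not tell that the category had been excluded.

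**Working it through.** No arithmetic applies, because the point concerns definitions. The check follows one event through the plan: a participant cannot take oral carbohydrate, intravenous glucose is given, and the session ends.

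1. **Is it handled by the safety procedures?** Section 10.1 describes the event and the response to it under the Safety heading. On the natural reading, yes.
2. **AE?** No. The exclusion in 10.3 names hypoglycaemia handled in this way and sets no upper limit of severity.
3. **SAE, SAR or SUSAR?** No. An SAE must first be an AE, and SAR and SUSAR must first be SAEs. The seriousness criteria are never reached.
4. **Device SAE?** No. Section 10.4 uses the definition in 10.3.
5. **NSAE?** No, by the explicit exclusion in 10.4. Without it the event would fit well, since intravenous glucose is an intervention that prevents a worse result.
6. **Does a reporting duty arise?** Under 10.3, collection and reporting apply to events that meet the AE definition; under 10.4, to events that meet the SAE or NSAE definition. The 24-hour notices, the reports to the authority and the EudraCT upload all follow from those definitions. The GCP unit's full monitoring (sections 11 and 19) names SAEs, so it does not reach the event either.
7. **Is it counted as an outcome?** Not as such. Section 8.2.1.4 lists nausea, headache, palpitation and vomiting. Sections 8.2.1.1 and 8.2.1.2 list carbohydrate interventions, time below 3.9 and 3.0 mmol/l, and episodes below 3.9 mmol/l. None separates severe events.
8. **Does it enter the comparison of treatments?** The terminated session does not, because section 9.2 requires two full sessions. The participant may be replaced (9.2) or the session rescheduled (12).

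The protocol text contains no other safety-reporting route for the event. The list in section 12 names severe hypoglycaemia apart from adverse events. That is consistent with the literal reading but does not prove it, since items in a list can overlap.

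**The case against.** The strongest reply is that the phrase on safety procedures is never defined. Section 10.1 refers to SOP_Dysglycemia, which is only listed as an appendix and may contain its own reporting rule. Section 17 describes staff action, including intravenous glucose, as a way to avoid or prevent a severe episode. On that view a severe episode is a failure of the procedures and lies outside the exclusion. This stands as an ambiguity. It does not remove the point, because 10.1 itself sets out the handling of the severe event, and a reporting rule in the SOP would conflict with the definitions in 10.3 and 10.4 and would need to be reconciled with them.

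A reader might also draw stronger conclusions that the documents do not support:

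- *That the event disappears altogether.* Glucose values are still recorded. Section 9.2 requires data on non-completers in the final report, which section 21 sends to the ethics committee and the authority, although the content is not specified. A separate consequence, such as an injury or a seizure, could be an AE in its own right.
- *That the exclusion alone blocks expedited reports.* Even as an AE, the event would have to meet a seriousness criterion to be an SAE, and be unexpected and possibly or probably related to be a SUSAR. The link to device reporting through the NSAE class is more direct.
- *That there is no basis for stopping.* Section 12 names severe hypoglycaemia as a reason to discontinue and leaves termination of the whole study to the investigator's evaluation. Neither depends on AE status.
- *That one event means 1/20 = 5% reported as 0%.* The 20 are completers. A participant whose session was terminated and who was then replaced is not among them, so at least 20 + 1 = 21 would have started. The plan gives no expected rate.
- *That hyperglycaemia with raised ketones must also become an AE.* In section 10.2 a ketone value of 0.6 mmol/l or more prompts a system check and repeat measurement. Nothing there makes it an AE threshold.

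**Conclusion.** Wrong as written. Followed literally, sections 10.1, 10.3 and 10.4 together leave severe hypoglycaemia treated with intravenous glucose outside the AE, SAE, SAR, SUSAR and NSAE classes. The safety listing could therefore show none although one or more occurred, in either arm.

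The size cannot be given as a rate. What can be said is that the rule applies to every such event. The primary analysis is not changed by this point; what suffers is the safety account.

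The conclusion rests on two assumptions: that the safety procedures named in 10.3 and 10.4 include the severe-event paragraph of 10.1, and that the dysglycaemia SOP has no overriding reporting rule. If either fails, the protocol still needs a sentence that gives the status of these events.

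**What to change.** Reconcile sections 10.1, 10.3, 10.4 and 12 on the reporting status of severe hypoglycaemia:

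- In 10.3 and 10.4, limit the exclusions for hypoglycaemia to episodes that are not severe as section 10.1 already defines severe.
- State that a severe event is recorded as an AE and assessed for SAE, SUSAR and NSAE status by the existing criteria, with the existing reporting routes.
- Add to 8.2.1.4 the number of severe hypoglycaemic events by arm, counted over all started sessions, including those terminated or rescheduled.
- Make clear whether the termination in 10.1 refers to the session or to the trial, because section 5.4 attaches a duty to inform the authorities to premature termination of the study.
- Check that the dysglycaemia SOP agrees with the result.

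The change concerns reporting only; treatment stays as it is. The cost is about one sentence in each of 10.3 and 10.4, one line in 8.2.1.4, and a few extra reports of events that should be rare. No new measurement is needed.

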7.2. Study medication

7.2.1. Glucagon, GlucaGen®, Novo Nordisk, ATC code H04AA01

Please refer to the medication summary attached for further details including adverse reaction profile (section 4.8).

The product is commercially available by prescription and indicated for participants with T1D. The recommended glucagon dose for children above 10 years old living and acutely suffering from severe hypoglycemia is 1 mg administered as a subcutaneous or intramuscular bolus. The administration

may be repeated once if lack of clinical response. In this study, glucagon is delivered as microboluses up to every five minutes and the dose size is based on the current blood glucose value. It is expected that in this study the total daily glucagon dose will not exceed 1.0 mg per day. The glucagon pump is filled with freshly reconstituted glucagon 1 mg/ml every 13 hours, i.e. before study start and at 14:00 (other groups have reported uncomplicated use of glucagon with reconstitution intervals of up to 24 hours).

The effects of glucagon are not expected to extend beyond the course of the actual study days. Accordingly, no post-study follow-up is planned, but participants are encouraged to contact the sponsor if they experience or suspect any adverse events to the study medication in the 24 hours following discharge from the research unit. This also applies to participants who discontinue study participation.

Glucagon is ordered via the hospital's pharmaceutical service associated with the pharmacy of the Capital Region. Batch number, date of expiration and the amount used to fill the pump is noted in the participant eCRF.

7.2.2. Insulin, Fast-acting insulin aspart, FiAsp®, Novo Nordisk, ATC code A10AB05.

Please refer to the medication summary attached for further details including adverse reaction profile (section 4.8).

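### Section 10.3 counts drug adverse events for 50 minutes after a session, section 7.2.1 invites reports for 24 hours, and nothing says how the later reports are handled

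*Combined protocol and SAP*

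**What the plan says.** - **Section 10.3 (study medication).** The scope is broad: "All events meeting the definition of an AE will be collected and reported". The period is then described: "This includes events occurring during the clinical studies i.e. two times 26 hours, and in the 50 minutes following each study". The reason for the 50 minutes, five glucagon half-times, stands in the same sentence: "in the 50 minutes following each study (corresponding to five half-times for glucagon". At the end of the study, AEs and SAEs are uploaded to EudraCT.
- **Section 7.2.1 (glucagon).** Because glucagon is not expected to act beyond the study days, the plan states: "Accordingly, no post-study follow-up is planned". The same paragraph asks participants, including those who stop early, to get in touch with the sponsor "if they experience or suspect any adverse events to the study medication in the 24 hours following discharge from the research unit".
- **Section 10.4 (devices).** For SAEs and near-SAEs the period is the sessions only: "This includes events occurring during the clinical studies i.e. two times 26 hours".
- **Section 7.2.2 and the SUSAR definition in 10.3.** FiAsp is a study medication alongside GlucaGen, and expectedness is judged against the summaries of both products.
- **Sections 6.1 and 6.2.** Only participants and parents are blinded. Sessions start at 17:00, last 26 hours and are at least 36 hours apart. At the end, participants go back to their own pumps and sensors.

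**The concern.** For study-medication events the plan names two periods after a session, 50 minutes and 24 hours, and does not connect them. A participant who calls the sponsor three or twelve hours after going home is doing what 7.2.1 asks. Yet the event falls outside the period that 10.3 gives for collection, and no passage says whether it is recorded as an AE, assigned to an arm or included in the report to the authorities. As no other follow-up is planned, these calls are the only route by which later events could become known.

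The basis for the 50 minutes is also incomplete. It is a multiple of the half-time of one of the two study medications. On single-hormone days no glucagon is given and FiAsp is the only active drug, so the stated reason does not apply to that arm at all.

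At stake is the completeness of the AE/SAE listing and the EudraCT report in a small trial of adolescents. Without a rule, how a late report is handled would have to be settled case by case, by staff who are not blinded.

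**Working it through.** **Inputs.** Session 26 h = 1,560 min (6.2, 10.3). Post-session drug window 50 min (10.3). Invited reporting period 24 h = 1,440 min after discharge (7.2.1). Minimum separation of sessions 36 h (6.2). The plan gives no discharge time. I take discharge at session end as the base case and vary it in step 3.

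1. **The plan's own figures.** From 17:00 on day 1 to 19:00 on day 2 is 7 + 19 = 26 h, so the session length is consistent. 50 min / 5 = 10 min is the implied glucagon half-time, with 0.5^5 = 3.1% remaining after five. The documents give no half-time for glucagon or FiAsp, so the 50 minutes cannot be checked further. The drug window closes at about 19:50 on day 2, before the first night at home.

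2. **Share of the invited period outside the drug window.** (1,440 − 50) / 1,440 = 1,390 / 1,440 = 96.5%, or 23 h 10 min per session.

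3. **Sensitivity to discharge time.** If discharge is *d* minutes after session end, the overlap of the two periods is max(0, 50 − *d*). The share outside is 96.5% at *d* = 0 and rises to 100% at *d* = 50 or more. The base case is therefore the smallest value.

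4. **Share of session plus 24 h that is covered.** Drug events: (1,560 + 50) / (1,560 + 1,440) = 1,610 / 3,000 = 53.7%. Device events: 1,560 / 3,000 = 52.0%. The uncovered share for drug events passes one half only if the post-session period considered exceeds 1,560 + 2 × 50 = 1,660 min = 27 h 40 min.

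5. **Effect of aligning the window.** Drug collection would go from 26 h 50 min to 50 h per session, and from 53 h 40 min to 100 h over both.

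6. **Attribution to a session.** Reading the 36 h as running from the end of one session to the start of the next, a 24-hour tail closes at least 36 − 24 = 12 h before the second session. Each event then belongs to one session, and so to one arm.

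**The case against.** The strongest reply is that 10.3 promises to collect all AEs, and the sentence on timing opens with an inclusive phrase rather than a limit. The AE definition sets no time bound, SUSAR deadlines run from sponsor awareness, and recorded events are followed until stable or recovered. On that reading a late report would be captured anyway. This stands in part: the text does not expressly exclude late reports. But naming a period down to the minute, with a pharmacological reason, is most naturally read as setting a limit, and an ambiguity on this point still needs settling.

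It is also fair to say that a passive safety-net period may be longer than a systematic one, that FiAsp is used in both arms so that glucagon is the contrast of interest, and that later events are increasingly mixed with usual therapy. These points justify listing post-discharge events separately. They do not justify leaving their status open.

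Three stronger inferences are tempting, and the documents do not support them:

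- *Most of the at-risk period goes uncounted.* Over session plus 24 hours, 53.7% is covered for drug events and 52.0% for device events, and that part contains all closed-loop exposure. The 96.5% applies only to the 24 hours after discharge.
- *The comparison of adverse events between arms is cut short.* The symptom outcomes in 8.2.1.4 are defined by VAS rises. Section 6.2 describes the nausea VAS at set times during the visit, with vomiting scored at the maximum. No rating after discharge is described.
- *Section 10.4 contradicts 7.2.1.* The invitation concerns study medication and does not mention devices. A session-only device window is a narrow choice, not an inconsistency.

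**Conclusion.** The point holds as a mismatch between 10.3 and 7.2.1. On the natural reading of 10.3, at least 96.5% of the period in which participants are invited to report study-medication events lies outside the stated collection window, and reports from it would not enter the AE/SAE listing or the EudraCT report. The window also rests on glucagon's half-time alone in a trial with two study medications.

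This assumes that the period in 10.3 is meant as a limit and that discharge is at or after session end. The number of events affected cannot be estimated, because the documents give no rate for events after discharge. The primary outcome, the sample size and the VAS-based outcomes are unaffected. It is a modest defect in safety reporting, worth correcting because the correction is nearly free.

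**What to change.** Reconcile the two passages. In 10.3, define the collection window for study-medication AEs as the session plus the 24 hours after discharge already named in 7.2.1, and state that it also applies to participants who stop early. Replace the glucagon-only reason with one that covers both study medications. State that every event reported in the window is recorded and included in the EudraCT report.

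List post-discharge events by arm in a separate table from in-session events. They are reported spontaneously rather than observed by staff, so the two sets should not be pooled.

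The same window may be adopted for device SAEs and near-SAEs in 10.4 for consistency, but 7.2.1 does not require it.

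The cost is wording in 10.3 (and 10.4 if chosen) and the recording of reports that participants are already asked to make. No visits, samples or participants are added. The downside is a slightly higher AE count, with some events arising after the return to participants' own pumps; the separate table makes that visible.
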